## 9.2 SAMPLE SIZE DETERMINATION

We conducted a preliminary study using an alpha prototype of our cooling device in which subjects were blinded to the treatment. In that study, 56% of subjects in the dry air treatment group reported freedom from headache pain at two hours post treatment compared to 8% of subjects in the sham group. A power analysis using this effect size as a basis for calculation indicated a minimum sample size of 17 patients in each group would be required to achieve at least 80% power to detect a significant difference at two-tailed alpha level = 0.05. We realize that the effect size from this initial study seems quite large, and we propose a conservative  $n=25$  per group to account for error in estimates based on the preliminary results, for a total sample size of 75 subjects.

100 subjects will be consented to account for screen failures. Only the first 75 subjects who return with a qualifying migraine will be randomized to a treatment group.

## 9.3 POPULATIONS FOR ANALYSES

- **Intention-to-Treat (ITT) Population:** The Intention-to-Treat (ITT) population is defined as all randomized subjects. The ITT analysis population will be used as the primary analysis population for the primary endpoint.
- **Per Protocol (PP) Population:** The per-protocol analysis set (PP) includes all subjects in the ITT analysis set who received at least 10 minutes of treatment without any major protocol deviation. The PP analysis population will be used as the secondary analysis population for sensitivity analyses.
- **Safety Analysis Dataset:** The Safety population is defined as all randomized subjects who underwent the study intervention. This population will be used for the analysis of safety parameters.

## 9.4 STATISTICAL ANALYSES

### 9.4.1 GENERAL APPROACH

- **Categorical data summaries will include:**
  - Absolute (n) and relative (%) frequency tables
- **Continuous data summaries will include:**
  - Number of patients (n), the arithmetic mean and the standard deviation, the coefficient of variation as a percentage (CV%), the median, the interquartile range, the minimum and the maximum value.
- **Subject Disposition**
  - The disposition of all subjects who sign an ICF will be provided. The numbers of subjects screened, randomized, completed, and discontinued during the study, as well as the reasons for all post-treatment discontinuations will be summarized by treatment group. Disposition and reason for study discontinuation will also be provided as a by-subject listing.
- **Demographic and Baseline Characteristics**
  - Demographic and baseline characteristic data will be summarized descriptively and/or presented as a by-subject listing for the Safety Analysis population.
- **Protocol Deviations**
  - The deviations occurring during the clinical study will be summarized and/or presented as a by-subject listing.
- **Prior and Concomitant Medications**
  - Concomitant medications will be summarized separately for the Safety population. Descriptive summaries, by treatment group, will be prepared using the coded term. All concomitant medications recorded in the case report form will be listed.

---

#### 9.4.2 ANALYSIS OF THE PRIMARY EFFICACY ENDPOINT(S)

Both primary efficacy endpoints are scored categorically (Grade 0: no pain, Grade 1: mild pain, Grade 2: moderate pain, Grade 3 severe pain).

These categorical data will be summarized by absolute (n) and relative (%) frequency tables.

For categorical variables/proportions, we will perform Kruskal-Wallis test (the nonparametric equivalent of the ANOVA) to determine if there is a difference across the three study groups.

If there is a difference, then the Mann-Whitney test will be performed to compare the groups to each other to determine where the difference lies. We will correct for multiple comparisons using Bonferroni correction. The multiple imputation method will be used as the primary method for handling missing data in this study.

---

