## 1 PROTOCOL SUMMARY

### 1.1 SYNOPSIS

- Title:** A Transnasal Evaporative Cooling Device for Acute Treatment of Migraine
- Study Description:** This is a prospective, double-blind, sham-controlled, randomized study to assess the safety, tolerability, and optimal dose of the COOLSTAT Transnasal Thermal Regulating Device for acute treatment of migraine. The hypothesis is that evaporative cooling induced by the CoolStat using only ambient, dry air will reduce the pain and other symptoms of migraine headaches during an acute migraine episode.
- Objectives:**
- Primary Objective:
- To evaluate the safety, tolerability and optimal dose of the CoolStat for acute treatment of migraine
- Secondary Objectives:
- To assess the efficacy of CoolStat, by way of reduction in severity of reported pain and other symptoms post treatment compared to baseline.
  - To confirm the sham and the blinding procedures
  - To determine the treatment effect size to use in future sample size calculations for a pivotal randomized trial.

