#### Migraine prototype study:

A single-blinded, randomized trial was conducted at the Johns Hopkins Bayview Hospital headache clinic in Baltimore, MD, to study potential therapies for migraine, centered on evaporative cooling (Shah, 2021). This study evaluated the safety and efficacy of four potential therapies consisting of different air mixtures flowing in the nose and out the mouth: 1) a flow of dry oxygen, 2) a flow of dry air, 3) a flow of humidified oxygen, and 4) a flow of humidified air (control). All four gases were warmed to 37°C and delivered through a face mask (not the COOLSTAT device) with the study gases flowing in the nose and freely out of the mouth. The subjects were awake and otherwise healthy, excluding their migraine symptoms. The objective of the study was to assess safety and the ability to reduce symptoms from migraine.

Fifty-one (51) patients were enrolled in the study, of which 13 patients (mean age 49 years, 81% female) received humidified oxygen therapy and 9 patients (mean age 42 years, 82% female) received dry air therapy. Patients were randomized and blinded to their treatment group. There was significant pain relief at 2 hours post treatment compared to baseline reported by patients who received dry air, dry oxygen and humidified oxygen. Patients in the control group did not show significant pain relief from baseline to 2 hours post treatment.

A two-way ANOVA was conducted to examine the effect of gas type and moisture content in reducing headache symptoms in migraine (pain score reduction). There was a statistically significant interaction between the effects of gas type and moisture content on the headache score reduction,  $F(1,47) = 10.471$ ,  $p = 0.002$ . Simple main effects analysis showed that there were no significant differences between dry oxygen and dry air ( $p = 0.906$ ), but there were statistically significant differences between these gases when they were humidified ( $p < 0.001$ ).

No adverse events were reported in this study. It was concluded that high flow dry air is safe and appears to be effective in treating acute migraine pain and associated symptoms.

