#### Migraine dose escalation study:

A dose escalation and tolerability study was completed using the CoolStat device at the Johns Hopkins Bayview Hospital headache clinic in Baltimore, MD. 15 subjects experiencing migraine on the day of treatment were enrolled. Three air flow rates were tested and tolerability and efficacy were assessed for increasing air flow rates: 24 LPM, 36 LPM and 48 LPM. Five (5) subjects were tested at each flow rate, starting at the lowest flow rate (24 LPM). If the majority (3/5) of the subjects in the lowest flow rate group tolerated the full 10 minute treatment, the next group would receive an incrementally higher flow rate. All of the flow rates were found to be tolerable by study subjects, with 13 of the 15 subjects tolerating the full 10 minute treatment session. Although anecdotal (due to the small size of the study), there was also positive reports of reductions in migraine symptoms, which also appears to be related to flow, i.e., migraine symptoms reduced more with increased flow rates. 73% of the 15 subjects experienced pain relief immediately after treatment compared to baseline and 53% of subjects reported sustained pain relief at 2 hours post treatment. 67% of subjects reported that the benefit of the CoolStat treatment outweighed any discomfort they experienced during the treatment session and 73% said they would use the device again. 60% of subjects said the CoolStat works just as well or better than their current rescue medication. The adverse events that occurred were all graded as mild and anticipated (stuffy nose, burning sensation during treatment session) and resolved on their own. There were no serious adverse events or unanticipated device effects. This study demonstrated that the CoolStat is safe and tolerable for use in patients with acute migraine attacks.

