## 9 STATISTICAL CONSIDERATIONS

### 9.1 STATISTICAL HYPOTHESES

- Primary Efficacy Endpoint(s):
  1. Dose response comparison for pain relief at 2 hours

- a. Null hypothesis:  
 $H_0: \pi_A - \pi_S = 0$ ; where  $\pi_A$  is the proportion of subjects who show pain relief at 2 hours after active treatment (flow rate of x or Y) and  $\pi_S$  is the equivalent value for the sham-control treatment group.
  - b. Alternative hypothesis:  
 $H_a: \pi_A - \pi_S > 0$ ; where  $\pi_A$  is the proportion of subjects who show pain relief at 2 hours after active treatment (flow rate of x or Y) and  $\pi_S$  is the equivalent value for the sham-control treatment group.
- Secondary Efficacy Endpoint(s):
    1. Dose response comparison for pain relief immediately and 24 hours post treatment.
      - a. Null hypotheses:
        - i.  $H_0: \pi_A - \pi_S = 0$ ; where  $\pi_A$  is the proportion of subjects who show pain relief immediately after active treatment (flow rate of x or Y) and  $\pi_S$  is the equivalent value for the sham-control treatment group.
        - ii.  $H_0: \pi_A - \pi_S = 0$ ; where  $\pi_A$  is the proportion of subjects who show pain relief at 24 hours after active treatment (flow rate of x or Y) and  $\pi_S$  is the equivalent value for the sham-control treatment group.
      - b. Alternative hypothesis:
        - iii.  $H_a: \pi_A - \pi_S > 0$ ; where  $\pi_A$  is the proportion of subjects who show pain relief immediately after active treatment (flow rate of x or Y) and  $\pi_S$  is the equivalent value for the sham-control treatment group.
        - iv.  $H_a: \pi_A - \pi_S > 0$ ; where  $\pi_A$  is the proportion of subjects who show pain relief at 24 hours after active treatment (flow rate of x or Y) and  $\pi_S$  is the equivalent value for the sham-control treatment group.
    2. Dose response comparison for pain freedom immediately, 2 hours, and 24 hours post treatment.
      - a. Null hypotheses:
        - i.  $H_0: \pi_A - \pi_S = 0$ ; where  $\pi_A$  is the proportion of subjects who show pain freedom immediately after active treatment (flow rate of x or Y) and  $\pi_S$  is the equivalent value for the sham-control treatment group
        - ii.  $H_0: \pi_A - \pi_S = 0$ ; where  $\pi_A$  is the proportion of subjects who show pain freedom 2 hours after active treatment (flow rate of x or Y) and  $\pi_S$  is the equivalent value for the sham-control treatment group.

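### Two-hour pain relief is never defined by grade, so the primary test can be read two ways, and no dose-minus-sham estimate, confidence interval or baseline-grade adjustment is planned

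*Combined protocol and SAP*

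**What the plan says.** - **Hypothesis (9.1).** The primary efficacy parameter is the active-minus-sham difference in a proportion, where the active term "is the proportion of subjects who show pain relief at 2 hours after active treatment (flow rate of x or Y").
- **Scale (9.4.2).** "Both primary efficacy endpoints are scored categorically (Grade 0: no pain, Grade 1: mild pain, Grade 2: moderate pain, Grade 3 severe pain").
- **Test (9.4.2).** For categorical variables or proportions, "we will perform Kruskal-Wallis test (the nonparametric equivalent of the ANOVA) to determine if there is a difference across the three study groups". Mann-Whitney tests follow if the overall test shows a difference, with Bonferroni correction (number of comparisons not given) and multiple imputation for missing data. Section 9.4.3 carries the same methods to the secondary endpoints.
- **Meaning of relief.** The endpoint lists in 1.1 and 3 give no grade rule. The efficacy objective in 1.1 is worded "by way of reduction in severity of reported pain and other symptoms post treatment compared to baseline". Section 2.2 reports earlier studies in similar terms: "There was significant pain relief at 2 hours post treatment compared to baseline" and "73% of the 15 subjects experienced pain relief immediately after treatment compared to baseline".
- **Sample size (9.2).** The calculation uses pain freedom instead: 56% of the dry-air group "reported freedom from headache pain at two hours post treatment compared to 8% of subjects in the sham group".
- **Estimation.** Sections 1.1 and 3 list as a secondary objective "To determine the treatment effect size to use in future sample size calculations for a pivotal randomized trial". Sections 9.4.1 to 9.4.3 plan frequency tables, descriptive summaries and tests.
- **Baseline grade.** Section 8.1.2 records it and admits only Grades 2 and 3. Section 4.1 stratifies randomization by gender alone.

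**The concern.** Three links are missing between hypothesis, test and objective.

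First, a proportion with relief cannot be computed until relief is a rule on the grades. Reaching Grade 0 or 1 and falling by at least one grade are both natural rules. They disagree for every subject who goes from Grade 3 to Grade 2. A statistician following 9.4.2 could also rank the raw 2-hour grade, which answers a different question from 9.1.

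Second, an objective has no analysis attached to it. The pivotal-trial effect size needs an estimate with an interval, and only counts and p-values are planned.

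Third, the comparison makes no use of baseline grade. With 25 per arm and no stratification on grade, the arms may differ on it by chance, and any effect of that difference passes into the crude effect size.

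**Working it through.** **1. The plan's own figure.** Inputs from 9.2: 56% against 8%, two-sided 0.05, at least 80% power. Fisher's exact test, by full enumeration, gives power 77.4% at 16 per group and 81.3% at 17. The stated minimum of 17 is reproduced. The trial was therefore sized on two proportions, but for pain freedom rather than relief.

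**2. What the planned tests examine.**

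*On 0/1 relief.* Kruskal-Wallis equals Pearson chi-square times (N-1)/N. For 14, 11 and 6 responders of 25, chi-square is 5.389, and 5.389 × 74/75 = 5.317, the same as Kruskal-Wallis computed directly. On this coding the planned tests address 9.1.

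*On the 0-3 grade.* An illustration with 25 per arm, 5,000 runs, each test two-sided at 0.05, and relief taken as Grade 0-1:

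| Assumed distribution over Grades 0/1/2/3 | Relief | Mann-Whitney rejects | Proportion test rejects |
|---|---|---|---|
| Active .30/.10/.45/.15; sham .05/.35/.20/.40 | 40% vs 40% | 37% | 6% |
| Active .10/.46/.14/.30; sham .15/.17/.50/.18 | 56% vs 32% | 8% | 44% |

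These distributions were chosen to show that the two tests can part. Under a uniform shift in grade they would agree more closely.

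**3. Uncertainty at 25 per arm.** Wald half-width = 1.96 × √[(p₁q₁ + p₂q₂)/25].
- 56% vs 8% (9.2, pain freedom): 1.96 × √(0.3200/25) = 0.222
- 52% vs 32% (assumed): 1.96 × √(0.4672/25) = 0.268
- 50% vs 50% (assumed): 1.96 × √(0.5000/25) = 0.277

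Newcombe interval for 13/25 vs 8/25: the Wilson limits are 0.335 to 0.700 and 0.172 to 0.516.
- Lower: 0.20 - √[(0.52-0.335)² + (0.516-0.32)²] = -0.069
- Upper: 0.20 + √[(0.700-0.52)² + (0.32-0.172)²] = 0.433

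**4. What that means for a pivotal trial.** Per-arm n = [1.96√(2p̄q̄) + 0.842√(p₁q₁ + p₂q₂)]²/(p₁-p₂)², at 80% power and two-sided 0.05. For 52% vs 32%, (1.368 + 0.575)²/0.04 gives 95 after rounding up. At the upper limit (+43.3 points on a 32% sham rate) it is 20. At the lower limit there is no benefit to size for.

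**5. Baseline grade.** The documents give neither the Grade 3 share nor its association with outcome, so both are assumed.
- The chance that two arms of 25 differ by at least 5 subjects at Grade 3 (exact binomial) is 0.164, 0.193 and 0.203 at shares of 30%, 40% and 50%. For at least one of the two dose-sham pairs it is 0.278, 0.324 and 0.338.
- Suppose relief is 60% from Grade 2 and 30% from Grade 3, with no treatment effect. A 40% vs 60% split at Grade 3 gives 0.6×0.60 + 0.4×0.30 = 0.48 against 0.4×0.60 + 0.6×0.30 = 0.42, a spurious 6 points.
- In simulation (baseline log-odds 0 to 2, at least a 20-point Grade 3 excess in the dose arm, no true effect), the crude difference moves by about 0 to -11 points if relief is Grade 0-1, and by -3 to +13 if it is any drop. Even the direction depends on the definition.
- Over all trials the unadjusted test rejects in 5-7%. Most of the excess is discreteness: the uncorrected two-proportion test at 25 per arm rejects in 5.4%, 6.2% and 6.5% at common rates of 32%, 42% and 50% with no baseline effect at all.

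**The case against.** The strongest reply is that 9.4.2 names proportions among the variables to be tested and 9.1 defines the parameter as a proportion. Read together, they can mean Kruskal-Wallis on 0/1 relief, which is a chi-square test in all but a factor of 74/75. This stands. A reader might infer that rank tests are simply the wrong tests here, and the documents do not support that. What remains is that the sentence just before names the 0-3 grade, and that relief has no rule on either reading.

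A second reply is that the counts let anyone compute a crude difference and interval, and that planning an interval does not narrow it. Both statements are true. It would also be a prediction about the sponsor, not a finding, to say that the pivotal trial will be sized from bare percentages. The gap is that a stated objective has no prespecified estimate.

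A third reply is that an unadjusted randomized comparison is valid. This also stands. A reader might infer bias or an inflated error rate from the missing adjustment, but over all trials the test is close to nominal. The case rests on chance imbalance alone, with sizes that depend on assumptions. No benefit from adjusting for gender was shown.

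Finally, the phrases about change from baseline might be taken to define relief as any drop. Those in 2.2 describe other studies, and the one in 1.1 sets no size of drop.

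**Conclusion.** The concern holds for two points that rest on the text alone: relief has no grade rule, so the variable tested for the 9.1 hypothesis is open, and no dose-minus-sham estimate or interval is planned for a stated objective. The half-width of roughly 22 to 28 points shows how much uncertainty goes unreported. The 22-point figure uses the plan's own pain-freedom rates; the wider ones use assumed relief rates.

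The third point, baseline grade, is secondary. It is a cheap improvement using data already collected, and its size depends on an assumed Grade 3 share of 30-50% and an assumed baseline-outcome association. The documents support neither a claim that the planned tests are invalid nor one that the unadjusted comparison has a materially wrong error rate. The changes should be made before unblinding, but the trial does not depend on them to be interpretable.

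**What to change.** 1. Define 2-hour pain relief as a rule on the 0-3 grades, name that 0/1 variable as the one tested for the 9.1 hypothesis, and keep any rank test on the grade as supportive.
2. For each dose, report the risk difference against sham with a 95% interval. Give the crude difference with its Newcombe interval alongside, on observed cases. State which estimate will feed the pivotal trial.
3. Make the comparison CMH stratified by baseline grade, with the matching Mantel-Haenszel risk difference as the estimate in item 2. Both remain computable when one arm has no events, which at an 8% sham rate has probability 0.92²⁵ = 12%. Keep the Bonferroni correction and state its number of comparisons. If the overall test is kept, take it from the same stratified method. State how test and estimate are pooled over the planned imputations. Gender adjustment is optional. Give protection against chance imbalance, not power, as the reason.

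Cost: plan wording and a little programming, with no new data. Items 1 and 2 cost no power. For item 3, if baseline grade is not prognostic, simulation puts the loss at about 1-2 points of power at 0.05/3, and up to about 6 points in a single test at 0.05. Part of that loss reflects the unadjusted test running slightly above 5%.

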### 8.1.2 BASELINE/TREATMENT VISIT

Upon arrival to the headache clinic during the acute onset period of a migraine, the subject will complete a short questionnaire (migraine symptom questionnaire) rating headache pain on a 4-point scale (0 = no pain, 1 = mild pain, 2 = moderate pain, 3 = severe pain) and associated symptoms (nausea, photophobia and phonophobia) on a binary scale, as well report if their headache is unilateral, throbbing, and aggravated by physical activity. Only subjects with Grade 2 or Grade 3 pain at baseline may be randomized to receive study intervention.

A member of the study team will obtain the subject's height, weight, tympanic membrane temperature, blood pressure, and oxygen saturation and record findings in the Case Report Form.

The study team member will ask the patient to confirm that they are of general good health, other than their migraine diagnosis, and if there are any updates to the subject's medical history and record any concomitant medications.

If the subject meets the criteria for a qualifying migraine (Grade 2 or 3 severity, onset of head pain was less than 6 hours ago), the study team member will randomize the subject.

Upon setting up the device for a subject, the study team member who will administer the therapy will run a quick test to confirm the nebulizer is propelling mist into the CoolStat airstream. Once completing the device apparatus setup, they will turn the CoolStat on and hold a piece of paper up to the airstream for 5 seconds. If the paper becomes wet, then they can move forward with treatment. If it does not become wet, they should check the attachment interface of the nebulizer and nasal mask.

---

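### Section 9.4.2 uses neither baseline pain grade nor gender and plans no effect estimate with a confidence interval: a cheap improvement, not an error

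*Combined protocol and SAP*

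**What the plan says.** - **Tests.** Section 9.4.2 scores pain on Grades 0 to 3 and says "we will perform Kruskal-Wallis test (the nonparametric equivalent of the ANOVA) to determine if there is a difference across the three study groups". If that test is positive, "the Mann-Whitney test will be performed to compare the groups to each other to determine where the difference lies". On multiplicity: "We will correct for multiple comparisons using Bonferroni correction". The divisor is not stated. I read it as three pairwise tests, so 0.05/3 = 0.0167.
- **Summaries.** "These categorical data will be summarized by absolute (n) and relative (%) frequency tables". No section gives a treatment-effect estimate with a confidence interval.
- **Baseline grade.** Section 8.1.2 records pain before randomisation: "Only subjects with Grade 2 or Grade 3 pain at baseline may be randomized to receive study intervention".
- **Randomisation.** Section 4.1 stratifies by gender only. No analysis section uses gender or baseline grade. ANCOVA and LSMEANS appear only in the abbreviation list (10.2).
- **Objective.** Sections 1.1 and 3 list, as a secondary objective, obtaining an effect size for planning the pivotal trial.
- **Sample size.** Section 9.2 reports that "56% of subjects in the dry air treatment group reported freedom from headache pain at two hours post treatment compared to 8% of subjects", the 8% being the sham figure, and that the calculation "indicated a minimum sample size of 17 patients in each group would be required to achieve at least 80% power". It then takes 25 per group and concedes: "We realize that the effect size from this initial study seems quite large".

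**The concern.** Baseline severity on the same scale is a natural candidate predictor of the 2-hour grade, and it is already collected. With 25 per arm and no balancing on grade, chance differences between arms are likely. An unstratified rank test leaves that variation in the noise, and crude percentages carry it into the apparent effect.

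Two things are at stake: some power, if the true effect is smaller than planned, and the effect size handed to the pivotal trial, which will come from this one realised trial. The documents also allow three readings of relief: the 2-hour grade (9.4.2), a change from baseline (section 3) or a proportion (9.1). The size and sign of the power change depend on which applies. Settling that definition is a separate point.

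**Working it through.** **1. The plan's own figure.** Exact power of the two-sided Fisher test at 0.05 for 56% vs 8% is 77.4% at n=16 and 81.3% at n=17. The stated 17 is reproduced.

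**2. Effects examined** (high flow vs sham; low flow has half the log-odds).
- A, planned: logit(0.56) - logit(0.08) = 0.24 + 2.44 = 2.68.
- B, intermediate: 2.25, close to 45% vs 8% (-0.20 + 2.44 = 2.24).
- C, about half the planned effect: 1.3 (2.68/2 = 1.34).

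The 56% and 8% are pain-freedom rates. Applying them to the whole 0-3 scale assumes proportional odds.

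**3. Assumptions not in the documents.** Grade 3 share at baseline 30% or 50%. Sham distribution over Grades 0-3 of 12/24/38/27% or 8/15/32/45%. Log-odds for Grade 3 vs Grade 2 of 0, 0.6, 1.2 or 1.8 (odds ratios 1, 1.8, 3.3, 6.0). No dropout.

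**4. Power change from stratifying by grade**, in points, by simulation of three arms of 25. The procedure is the overall test at 0.05, then high flow vs sham at 0.0167. The log-odds within each baseline grade are held fixed.

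| Effect | Outcome | 0 | 0.6 | 1.2 | 1.8 |
|---|---|---|---|---|---|
| A | 2-hour grade | -0.2 | -0.1 to 0 | +0.3 to +0.5 | +1.2 to +1.8 |
| A | change score | +0.8 to +1.8 | +0.1 to +0.6 | -0.1 to +0.1 | -0.2 to -0.1 |
| B | 2-hour grade | -0.7 to -0.6 | -0.3 to 0 | +1.2 to +1.7 | +4.4 to +5.8 |
| B | change score | +2.8 to +5.0 | +0.7 to +1.8 | -0.2 to +0.2 | -0.7 to -0.2 |
| C | 2-hour grade | -1.9 to -1.8 | -0.6 to -0.1 | +2.7 to +3.9 | +7.4 to +9.5 |
| C | change score | +6.7 to +8.7 | +2.6 to +3.3 | -0.6 to +0.4 | -1.5 to -0.7 |

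Break-even for the 2-hour grade is at log-odds of about 0.6 to 0.9 (odds ratio 1.8 to 2.5). For binary relief, over A to C, the change is -1.1 to +5.6 if relief means Grade 0/1 at 2 hours, and -1.7 to +3.5 if it means at least one grade lower.

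**5. Same check with marginal rates held fixed.** Fixing the within-grade log-odds lets the overall effect shrink as grade strength rises. With 8% of sham at Grade 0, the high-flow Grade 0 rate under A falls from 56% to 48-51% at log-odds 1.8. Holding the marginal Grade 0/1 rates fixed instead, the largest gain for the 2-hour grade is about +0.4 at A and about +2 at B. At C it is about +3 to +4 at log-odds 1.2 and +8 to +11 at 1.8.

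**6. Type I error.** The overall test rejects in about 4.6 to 5.4% of null trials, stratified or not.

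**7. Chance imbalance.** With two arms of 25, a gap of 5 or more patients (5/25 = 20 points) in the Grade 3 share has exact binomial probability 16.4% (30% at Grade 3) to 20.3% (50%) per pair. Given such a gap, at effect C and across the four grade strengths, the crude risk difference shifts by 0 / 3 / 6 / 8-10 points if relief is Grade 0/1. If relief is at least one grade lower, it shifts by 7-8 / 4-5 / 1-3 / 0-1 points the other way. The Mantel-Haenszel difference shifts by 0.4 points or less. The sampling SDs at effect C are 12.6-13.7 (crude) and 12.2-13.6 (Mantel-Haenszel).

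**8. Crossing gender with grade.** At the 80% women expected in section 5.4, each arm has about 25 × 0.20 = 5 men. The chance that some arm has an empty male cell is 1 - (1 - 2×0.5^5)^3 = 0.18 with 50% at Grade 3, and 1 - (1 - 0.7^5 - 0.3^5)^3 = 0.43 with 30%.

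**The case against.** The case for leaving the plan alone is fair. The tests are legitimate, type I error is controlled, and the unadjusted difference is unbiased over randomisations. At the planned effect, graded power is about 97-99% either way. The gain depends on a prognostic strength that the documents do not give. On the change-score reading the endpoint already contains baseline. Stratifying hardly improves precision, and the imbalance shift is smaller than the sampling SD. Baseline characteristics are tabulated anyway (9.4.1, 9.4.5), so a gap could be seen. Coverage of a stratified interval in small strata has not been checked here.

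All of that stands, and it sets the weight of the point. It does not remove the case. A table shows an imbalance without giving an estimate that allows for it, and an adjustment chosen after seeing the gap is less credible than one fixed beforehand.

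Two stronger readings are tempting and not supported:
- **That stratifying makes power insensitive to prognostic strength.** It looks so only with the within-grade log-odds fixed. With marginal rates fixed at B, unstratified power stays at 96-97% and stratified power moves from about 96% to 99%.
- **That B is the effect 25 per arm can just detect.** The 80% power for 45% vs 8% belongs to a Fisher test at 0.05, which 9.4.2 does not use. The plan's graded procedure has about 89-97% power there.

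**Conclusion.** The point holds as an optional, low-cost improvement. A reader might infer that omitting baseline grade invalidates the tests or biases the comparison. It does neither.

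For the 2-hour grade, over grade log-odds of 0 to 1.8:
- planned effect: about -0.2 to +2 points (at most about +0.4 with marginal rates fixed);
- log-odds 2.25: about -0.7 to +6 (at most about +2 with marginal rates fixed);
- half the planned effect: about -2 to +11 under either convention.

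These figures rest on the assumed sham distributions, Grade 3 shares, proportional odds and grade strengths. A stronger prognostic effect would give more, so they are not ceilings. On the change-score reading the pattern reverses. The trade is asymmetric: about 2 points at most to lose, and several to gain if the effect is smaller than planned and grade is clearly prognostic.

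The firmer return is a pre-specified effect estimate with a CI that a chance imbalance in grade does not shift. The missing estimate matters whatever the power gain, because the trial has an effect-size objective.

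**What to change.** In section 9.4.2, before unblinding:

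1. Stratify the overall and pairwise tests by baseline grade (two strata). Use van Elteren type tests if the outcome is graded (three-group version with 2 df, then pairwise), or Cochran-Mantel-Haenszel tests if it is binary. Keep the Bonferroni correction.
2. Report a grade-stratified effect estimate with a 95% CI for each active arm vs sham: the Mantel-Haenszel risk difference for binary relief, or the common odds ratio from a proportional-odds model with baseline grade if graded.
3. Add one supportive model with treatment, grade and gender. Do not cross gender and grade as strata, because of the empty cells shown above.
4. Keep the unadjusted tests as sensitivity analyses.

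The cost is SAP wording and a few lines of code, since both variables are already collected. The price in power is up to 1.9 points on the 2-hour grade if grade is not prognostic. If grade is strongly prognostic, it is up to 1.5 points on a change score and 1.7 on binary relief defined as at least one grade lower.
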